
The overall design of the current study is consistent with previously published opioid agonist challenge studies, which have investigated the opiate blocking effects of BPN (Jasinski et al., 1978; Walsh et al., 1995). Based on the pharmacokinetic profile of CAM2038 q1w, specifically that BPN peak plasma concentrations are observed within the first 24 hours post-dose,

Version: 2.0, 17NOV2015 Page 42 of 99

Hydromorphone Challenge Sessions will begin a minimum of 24 hours following the first dose of CAM2038 q1w. An additional Hydromorphone Challenge Session will be administered after 48, 72, 96, 120, and 144 hours post-dose in order to investigate the full duration and magnitude of opioid-blockade of the CAM2038 q1w formulation. In order to improve subject retention, the study drug will be administered for two weeks with two sets of three Hydromorphone Challenge Sessions per week; thereby reducing the inpatient Treatment Phase and the overall duration of the study.

In the current study, subjective "at the moment" assessments using VAS for Drug Liking, Feeling High, Any Drug Effects, Good Drug Effects, Bad Drug Effects, Sedated, and Desire to Use Opioids will be included to measure the degree and time course of the CAM2038 q1w-induced blockade of subjective effects. In addition, pharmacokinetic samples will be collected on each Hydromorphone Challenge Session day to measure plasma levels of BPN and norbuprenorphine prior to the challenge session.

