#### 12.3.3.1. Primary Efficacy Analyses

The primary efficacy variable will be  $E_{max}$  of Drug Liking VAS. This variable will be analyzed via a mixed model including subject, challenge dosing (A=0 mg, B=6 mg, or C=18 mg), Period (1, 2, or 3 to indicate first, second, or third day of each challenge session), challenge session (1, 2, 3, or 4), where subject will be treated as random effects and the remaining parameters fixed effects. The estimated treatment effects, differences in treatment effects (test dose – the reference

Version: 2.0, 17NOV2015 Page 71 of 99

dose of 0 mg), 95% confidence intervals of the differences will be presented. Blockade effects will be claimed if upper bound of the treatment difference is  $\leq 11$ .

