9.1.2 PRIMARY ANALYSIS

The primary analysis of the primary efficacy variable, E_{\max} of drug liking VAS, will be performed using the completer population. This variable will be analyzed via a mixed model including sequence (ABC, ACB, BAC, BCA, CAB, CBA), dosing (challenge dosing A=0 mg, B=6 mg, or C=18 mg), period (1, 2, or 3 to indicate first, second, or third day of each challenge session), session (challenge session 1, 2, 3, or 4), and dosing-by-session interaction as fixed effects, and subject as random effects. The maximum likelihood estimation will be used to estimate the parameters. Specifically, the following pseudo SAS codes will be used for the analysis:

```
proc mixed data=Efficacy_Data method=ml;
class SubjectID ChallengeDose Sequence Period Session;
model Emax=Sequence ChallengeDose Period Session ChallengeDose*Session;
random SubjectID / Subject= SubjectID;
LSMEANS ChallengeDose*Session/diff cl alpha=0.05;
Run;
```

The estimated treatment effects, differences in treatment effects (test dose – the reference dose of 0 mg), 95% confidence intervals of the differences will be presented. Blockade effects will be claimed if the upper bound of the treatment difference is ≤ 11 .

The same methodology will be used to analyze CAM2038 q1w 24 mg and 32 mg separately.

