9.4 ADJUSTMENTS FOR MULTIPLICITY

The study involves multiple comparisons. Procedures will be used to control for the overall Type I error rate at the significance level of 0.05. The following ordered comparisons of blocking effect will be tested at the 0.05 level of significance:

1. Hydromorphone 6 mg vs Hydromorphone 0 mg for CAM2038 q1w 32 mg;
2. Hydromorphone 6 mg vs Hydromorphone 0 mg for CAM2038 q1w 24 mg;
3. Hydromorphone 18 mg vs Hydromorphone 0 mg for CAM2038 q1w 32 mg;
4. Hydromorphone 18 mg vs Hydromorphone 0 mg for CAM2038 q1w 24 mg;

Blockade effect cannot be claimed unless all preceding blocking effects, if any, are established.

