9.6 POWER AND SAMPLE SIZE JUSTIFICATION

A sample size of 24 subjects will provide 90% power for the CAM2038 32 mg to demonstrate no significant difference in the mean E_{\max} score of the Drug Liking VAS comparing to 0 mg hydromorphone at a two-sided 0.05 significance level with a non-significant difference cutoff at ≤ 11 points. In the sample size calculation it was assumed that the true difference was less than or equal to 1.5 and the standard deviation was 9.8.

Additional 24 subjects will be enrolled to CAM2038 24 mg group. This sample size will provide approximately 83% power for the CAM2038 24 mg to demonstrate no significant difference in the mean E_{\max} score of the Drug Liking VAS comparing to 0 mg hydromorphone at a two-sided 0.05 significance level with a non-significant difference cutoff at ≤ 11 points. In the sample size calculation it was assumed that the true difference was less than or equal to 2.5 and the standard deviation was 9.8.

The plan will be to enroll a sufficient number of subjects to ensure that approximately 48 subjects complete the study (24 subjects per treatment group) by over-enrollment as needed.

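### The SAP's primary analysis produces four session-specific upper bounds per comparison, and nothing says which of them decides the blockade claim

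*SAP*

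**What the plan says.** SAP 9.1.2 models Emax of Drug Liking with fixed effects for sequence, dose, period, session and dose-by-session, fitted by maximum likelihood separately in each CAM2038 group. The only random term is "random SubjectID / Subject= SubjectID", which is a subject intercept. The only output statement is "LSMEANS ChallengeDose*Session/diff cl alpha=0.05".

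The decision rule is written for one quantity: "Blockade effects will be claimed if the upper bound of the treatment difference is" at most 11.

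SAP 9.4 promises that "Procedures will be used to control for the overall Type I error rate at the significance level of 0.05" and lists four ordered comparisons. The first is "Hydromorphone 6 mg vs Hydromorphone 0 mg for CAM2038 q1w 32 mg"; none carries a session index. A comparison can be claimed only if every earlier one succeeded, so each step needs one yes or no.

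SAP 9.6 powers one mean difference per CAM2038 group. For 32 mg, "it was assumed that the true difference was less than or equal to 1.5 and the standard deviation was 9.8", giving 90% with 24 subjects. For 24 mg the assumed difference is 2.5, giving about 83%.

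Protocol 12.3.3.1 has no interaction. It lists subject, dose, period and session, "where subject will be treated as random effects and the remaining parameters fixed effects", which yields one difference per hydromorphone dose. Protocol 7.2, however, spreads the challenges over the dosing week "in order to investigate the full duration and magnitude of opioid-blockade of the CAM2038 q1w formulation".

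**The concern.** Adding the interaction turned one dose difference into four, but the claim rule, the test sequence and the power statement were not changed to match. At least three rules fit the output: one session suffices, all four must pass, or the average decides. They are different hypotheses with different error rates and power. Without a stated choice, no step in SAP 9.4 has a defined result, the 0.05 control promised there is not assured, and the choice could be made with the data in view.

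A second defect bears on any repair. A subject intercept alone treats a subject's dose differences in the four sessions as independent. If a subject who is incompletely blocked in one session tends to be so in the others, the coded bounds are too narrow, and the averaged bound suffers most.

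**Working it through.** **1. Count the bounds.** Three doses × four sessions = 12 cells, giving 12 × 11 / 2 = 66 pairwise differences. Eight of these compare an active dose with 0 mg in the same session: four for 6 mg and four for 18 mg. Over two CAM2038 groups that is 16 upper bounds for the four decisions in SAP 9.4.

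**2. Reproduce the stated power (SAP 9.6).** Take a two-sample t contrast with n = 24 per dose, SD 9.8, cutoff 11, 0.025 on the upper bound and 46 df.
- SE = 9.8 × √(2/24) = 2.829.
- 32 mg: (11 − 1.5)/2.829 = 3.358, power 90.8% (stated 90%).
- 24 mg: (11 − 2.5)/2.829 = 3.005, power 83.7% (stated about 83%).

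The figures reproduce for one test of one difference, so the sample size presupposes a single bound.

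**3. The readings can disagree on the same data.** One illustrative dataset had 24 subjects and between- and within-subject SDs of 6.93 (total √2 × 6.93 = 9.8). The true 18 mg difference was 1.5, raised by 10 in session 1. Fitted with the SAP model, the 18 mg upper bounds were 20.3, 8.2, 9.5 and 3.3. The session average, which the code does not request, had an upper bound of 8.4; the protocol model gave 8.6. These data fail under all-four and pass under any-session or average.

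In repeated simulation of the coded model with true differences 1.5, 1.5, 1.5 and 15 (assumed, within-subject correlation 0), blockade was claimed in 99.9% (any), 99.1% (average) and 0.02% (all four) of trials.

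**4. Error rates.** The documents give no correlations, so r, the correlation of a subject's session differences, is varied. The design has 24 subjects, six sequences (the same sequence in every session, assumed) and 288 observations. The true difference is 11 in every session, except in the all-four row, where one session is at 11 and the others at −5 (assumed). Nominal error is 2.5%; 60,000 runs.

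| Coded model (intercept, ML) | r = 0 | 0.25 | 0.5 | 0.75 | 0.9 |
|---|---|---|---|---|---|
| Any session | 10.7% | 11.5% | 11.7% | 10.7% | 9.5% |
| One given session | 2.8% | 3.3% | 4.0% | 4.7% | 5.5% |
| All four | 2.9% | 3.3% | 3.9% | 4.7% | 5.3% |
| Average | 2.8% | 8.2% | 13.4% | 17.5% | 20.1% |

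With a subject-by-dose random term and REML, the ranges over r are 2.4–2.8% (one session), 2.5–2.7% (all four) and 1.9–2.6% (average).

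**5. Why the average is hit hardest.** Let v be the within-subject variance of one observation.
- True variance of the averaged difference: (2v/24) × (1 + 3r)/4.
- Variance used by the coded model: (2v/24) × c/4, where c is its expected residual variance relative to v.
- Of the 251 residual df, 44 carry subject-by-dose variation (four observations per subject and dose) and 207 do not. ML divides by 264. So c = (251/264) × [1 − r + (44 × 4/251) r].
- At r = 0.5, c = 0.951 × (0.5 + 0.351) = 0.809. The true variance is 2.5/0.809 = 3.09 times the coded one and the true SE 1.76 times. The error is about Φ(−1.969/1.76) = 13%, in line with the table.
- At r = 0, c = 0.951 and the error is about 2.7%, which is the ML effect alone.

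**6. Power if all four sessions must pass.** Take SD 9.8 per observation, r = 0 and the corrected model. With within-subject correlation ρ, SE = 2.829 × √(1 − ρ). Power is about [Φ((11 − δ)/SE − 1.971)]⁴, δ being the true difference.

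| ρ | 32 mg (δ = 1.5) | 24 mg (δ = 2.5) |
|---|---|---|
| 0 | 0.917⁴ = 71% (simulated 70%) | 0.849⁴ = 52% (52%) |
| 0.3 | 0.979⁴ = 92% (92%) | 0.947⁴ = 81% (81%) |
| 0.5 | 0.997⁴ = 99% (99%) | 0.989⁴ = 96% (95%) |

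Against the stated 90% and 83%, the shortfall is gone for 32 mg at ρ = 0.3 and for 24 mg by 0.5.

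**The case against.** The strongest reply is that a pooled contrast is meant. The claim rule is singular, the difference is described as test dose minus 0 mg with no session, SAP 9.4 has no session index, and the protocol model gives one difference per dose. The SAP calls its code pseudo code, and the average can be estimated from the same fit. All of this is fair and makes the average the likeliest intention. It still leaves the intention unstated: the SAP added the interaction, requested only session-level output, and is the document to which Protocol 12 defers for the final analysis.

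Three further points stand in part.
- No passage supports an any-session rule, so the 9.5–11.7% error shows what the wording leaves open, not what is planned. The 1.5/1.5/1.5/15 case was chosen to separate the rules.
- The variance defect is a separate matter from which bound decides, and its size depends on r, which the documents do not give. At r = 0 it is negligible. It belongs here because naming the average without correcting the variance could leave an anti-conservative primary test.
- The all-four power loss is large only when within-subject correlation is low, which sits oddly with fitting a random subject effect.

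The titles of Table 14.2.1.1a and Figure 14.1.1.2 are weak evidence either way. Neither names the deciding contrast.

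**Conclusion.** The concern holds. Followed as written, the plan gives four bounds where its claim rule, test order and power each need one, and no text elsewhere in the SAP or protocol selects among them. This needs no assumption; it follows from the model, the output statement and the rule.

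The consequences do depend on assumptions: balanced sequences repeated in each session, SD 9.8 per observation, and ranges for correlations that the documents omit. Under these, error at the margin runs from near nominal (about 2.8%) to 20.1%, depending on the reading and on r. All-four power for 32/24 mg runs from 70%/52% to 99%/95% as ρ goes from 0 to 0.5. The stated power is not an arithmetic error; it is correct for a single contrast. This should be settled before database lock and unblinding.

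**What to change.** Name one deciding contrast per gated step in SAP 9.1.2 and 9.4, choosing one of these:

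1. **Session-averaged dose difference**, matching Protocol 12.3.3.1. Add `LSMEANS ChallengeDose/diff cl alpha=0.05;` and report the session bounds descriptively. Power with the corrected variance is at least 98.5%/96.0% (32/24 mg) for r = 0 and 0.5. It falls to about 95%/90% at r = 0.75 and 93%/86% at r = 0.9 (within-subject correlation 0), still above plan.
2. **All four session bounds at most 11**, with no alpha adjustment. Restate the power in SAP 9.6 for this rule.
3. **Separate session claims.** Add a session order or alpha split to SAP 9.4 and say which session result opens the next gate. With alpha split over four sessions, per-session power (r = 0) is about 80%/68%, 93%/86% and 99%/96% at within-subject correlation 0, 0.3 and 0.5.

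Under every option, replace the RANDOM line with `random intercept ChallengeDose / subject=SubjectID;` and use `method=reml`. Without this, even option 2 errs up to about 5%.

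A minor addition: state in SAP 9.4 that its test order replaces that of Protocol 12.3.6. Both are valid fixed sequences.

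The cost is one SAP revision, which SAP 3.0 allows before lock: a sentence each in 9.1.2 and 9.4, up to three code lines, and for option 2 a revised power statement. No protocol amendment, new data or extra subjects are needed.

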9.1.3 MISSING VALUE IMPUTATION

Missing scores will not be imputed, unless otherwise stated.

9.1.4 SUPPORTIVE ANALYSES

As a supportive analysis, the primary efficacy variable will be analyzed based on ITT subjects using the same methodology.

9.2 SECONDARY EFFICACY OUTCOMES

In addition to the primary endpoint of change from baseline in E_{\max} of Drug Liking VAS, the following secondary endpoints will be calculated:

- High VAS E_{\max}
- Good Effects VAS E_{\max}
- Bad Effects VAS E_{\max}
- Sedated VAS E_{\max}
- Any Effects VAS E_{\max}
- Desire to use VAS E_{\max}

All these variables will be analyzed via the same methodology used to analyze the primary efficacy variable.

The follow secondary efficacy variables will be summarized by CAM2038 treatment group on the scheduled days that they are measured:

- Clinician-Rated Opioid Withdrawal Scale (COWS);
- Subjective Opioid Withdrawal Scale (SOWS);

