Severity of Opioid Withdrawal VAS					X dd		X			
Check-in		X								
Discharge									Xee	

BMI=body mass index; COWS=Clinical Opiate Withdrawal Scale; C-SSRS=Columbia-Suicide Severity Rating Scale; DSM-V = Diagnostic and Statistical Manual of Mental Disorders – Fifth Edition; ECG=electrocardiogram; ET=Early Termination; FSH=Follicle Stimulating Hormone; HIV= Human Immunodeficiency Virus; MADRS=Montgomery-Asberg Depression Rating Scale; OOWS=Objective Opioid Withdrawal Scale; PD=pharmacodynamic VAS=visual analog scale.

- y Blood samples will be taken pre-dose and 1, 4, 6 and 8 hours after CAM2038 q1w injection
- z Blood samples will be taken approximately 60 minutes prior to administration of hydromorphone on each of the 3 Hydromorphone Challenge Session days during the Treatment Phase (i.e., Days 1, 2, 3, 4, 5, 6, 8, 9, 10, 11, 12, and 13).
- aa Blood samples will be taken approximately 168 hours after CAM2038 q1w injection
- bb Pharmacodynamic training may be administered as frequently as required, but all subjects must complete at least one training session prior to the Qualification/Baseline Hydromorphone Challenge Session. Training can only occur prior to or after, but not during the Hydromorphone Challenge Sessions.
- cc On Hydromorphone Challenge Session days (i.e., Day -3, -2, -1, 1, 2, 3, 4, 5, 6, 8, 9, 10, 11, 12, and 13), subjective measures (Drug Liking, Feeling High, Any Drug Effects, Good Drug Effects, Bad Drug Effects, Sedated, Desire to Use Opioids VAS) assessments will be performed at predose (up to 15 minutes prior to dosing) and at 5, 10, 15, 30, 45, 60, 75, 90, 120, 150, 180, 210, 240, 270 and 300 minutes post-dose.
- dd Severity of Opioid Withdrawal VAS will be administered, as needed, if a subject experiences precipitated withdrawal following administration of CAM203 q1w.
- ee Subjects will be discharged on Day 14, if medically acceptable.

Version: 2.0, 17NOV2015 Page 40 of 99

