# 10.5. Appropriateness of Measures

As the primary objective of this study is to demonstrate CAM2038 q1w-induced blockade of hydromorphone effects; Drug Liking VAS has been chosen as the primary pharmacodynamic variable.

The Drug Liking VAS assesses the response to the question "At this moment, I like this drug." Values for this scale range from 0 ("Strong disliking") to 100 ("Strong liking"), with 50 as the neutral point ("Neither like nor dislike"). This scale has been included to understand the time course of CAM2038 q1w-induced blockade of subjective effects of hydromorphone. Additional subjective effects VASs will be collected to support findings on the primary measure. The subjective effects VAS items will measure positive (Good Drug Effects and High), negative (Bad

Version: 2.0, 17NOV2015 Page 64 of 99

Drug Effects), and other subjective effects (Any Drug Effects, Desire to Use Opioids, and Alertness/Drowsiness VAS) to further assess the pharmacologic response to the Hydromorphone Challenge Session injection.

Pharmacokinetic measures are included to confirm exposure, explore potential relationships between pharmacokinetic and subjective measures, and if necessary, to aid in the interpretation of unusual responses.

Standard safety outcomes, such as AEs, ECG, vital signs and clinical laboratory testing will be assessed during the study. In addition, respiratory rate and oxygen saturation safety monitoring will be included prior to dosing with IR morphine 30 mg and after dosing with hydromorphone.

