9.0 EFFICACY ANALYSES

Many of the efficacy variables are visual analog scale (VAS) based. Each VAS will be scored as an integer from 0 to 100. When appropriate, VASs will be administered as bipolar measures, meaning

that the neutral point equals 50 (i.e., Drug Liking and Alertness/Drowsiness VAS). The neutral point will also be labeled with an anchor, such as “neither like nor dislike.” Unipolar VASs (i.e., High, Good, Bad, and Any Effects VAS) are presented with anchors such as “not at all” (score = 0) to “extremely” (score = 100), where the neutral point equals 0. The use of unipolar scale is determined by the nature of the subjective effect being measured. If precipitated withdrawal occurs after administration of CAM2038, patients will have a unipolar VAS assessment of opioid withdrawal severity.

The table lists the subjective effects VAS question text and response anchors.

Interpretation	Include Pre-dose	Description	Question Text	Response Anchors
Balance	No	Drug Liking	At this moment, my liking for this drug is	0: Strong disliking 50: Neither like nor dislike 100: Strong liking
Other effects	No	Any Drug Effects	At this moment, I feel any drug effects	0: Not at all 100: Extremely
Positive	Yes	High	At this moment, I feel high	
Positive	No	Good Drug Effects	At this moment, I feel good drug effects	
Negative	No	Bad Drug Effects	At this moment, I feel bad drug effects	
Other Effects	Yes	Desire to use opioids	At this moment, I desire opioids	0: Definitely not 100: Definitely so
Other Effects	Yes	Alertness/Drowsiness	At this moment, my mental state is	0: Very drowsy 50: Neither drowsy nor alert 100: Very alert

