9.1.1 DERIVATION OF E_{MAX} DRUG LIKING VAS

Four hydromorphone challenge sessions (3 consecutive days each with dose randomized) will be conducted on Days 1 to 3, Day 4 to 6, Days 8 to 10, and Days 11 to 13 after the first CAM2038 administration. Each Hydromorphone Challenge Session will consist of 3 doses of hydromorphone 10 mg/mL IM injections (doses of 0 mg [placebo], 6 mg and 18 mg) administered on 3 consecutive days in randomized order. The drug liking VAS will be rated by the subjects at predose and at 5, 10, 15, 30, 45,

60, 75, 90, 120, 150, 180, 210, 240, 270 and 300 minutes post-dose. The primary efficacy variable E_{\max} of drug liking VAS will be the maximum of the above post-dosing drug liking VAS scores.

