TABLE 14.2.4.2a	Analysis Results for Primary Efficacy Variable Emax of Bad Effects VAS for CAM2038 32 mg (ITT Population)

TABLE 14.2.4.2b	Analysis Results for Primary Efficacy Variable Emax of Bad Effects VAS for CAM2038 24 mg (ITT Population)
TABLE 14.2.5.1a	Analysis Results for Primary Efficacy Variable Emax of Sedated Effects VAS for CAM2038 32 mg (Completer Population)
TABLE 14.2.5.1b	Analysis Results for Primary Efficacy Variable Emax of Sedated Effects VAS for CAM2038 24 mg (Completer Population)
TABLE 14.2.5.2a	Analysis Results for Primary Efficacy Variable Emax of Sedated Effects VAS for CAM2038 32 mg (ITT Population)
TABLE 14.2.5.2b	Analysis Results for Primary Efficacy Variable Emax of Sedated Effects VAS for CAM2038 24 mg (ITT Population)
TABLE 14.2.6.1a	Analysis Results for Primary Efficacy Variable Emax of Any Effects VAS for CAM2038 32 mg (Completer Population)
TABLE 14.2.6.1b	Analysis Results for Primary Efficacy Variable Emax of Any Effects VAS for CAM2038 24 mg (Completer Population)
TABLE 14.2.6.2a	Analysis Results for Primary Efficacy Variable Emax of Any Effects VAS for CAM2038 32 mg (ITT Population)
TABLE 14.2.6.2b	Analysis Results for Primary Efficacy Variable Emax of Any Effects VAS for CAM2038 24 mg (ITT Population)
TABLE 14.2.7.1a	Analysis Results for Primary Efficacy Variable Emax of Desire to Use VAS for CAM2038 32 mg (Completer Population)
TABLE 14.2.7.1b	Analysis Results for Primary Efficacy Variable Emax of Desire to Use VAS for CAM2038 24 mg (Completer Population)
TABLE 14.2.7.2a	Analysis Results for Primary Efficacy Variable Emax of Desire to Use VAS for CAM2038 32 mg (ITT Population)
TABLE 14.2.7.2b	Analysis Results for Primary Efficacy Variable Emax of Desire to Use VAS for CAM2038 24 mg (ITT Population)
TABLE 14.2.10.1a	Summary of Change from Baseline in Clinical Opiate Withdrawal Scale (COWS) for CAM2038 32 mg (Completer Population)
TABLE 14.2.10.1b	Summary of Change from Baseline in Clinical Opiate Withdrawal Scale (COWS) for CAM2038 24 mg (Completer Population)
TABLE 14.2.10.2a	Summary of Change from Baseline in Clinical Opiate Withdrawal Scale (COWS) for CAM2038 32 mg (ITT Population)
TABLE 14.2.10.2b	Summary of Change from Baseline in Clinical Opiate Withdrawal Scale (COWS) for CAM2038 24 mg (ITT Population)
TABLE 14.2.11.1a	Summary of Change from Baseline in Objective Opioid Withdrawal Scale (OOWS) for CAM2038 32 mg (Completer Population)

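### The Sedated VAS endpoint has no defined scale, and on the only sedation-type scale in the plan the Emax and upper-bound rule point away from sedation

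*SAP*

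**What the plan says.** Emax of the Sedated VAS is a secondary endpoint in the Protocol Synopsis, Protocol 10.7.2 and 12.3.3.2, and SAP 9.2. SAP Appendix A plans four tables for it (14.2.5.1a to 14.2.5.2b). Sedated is also named where the assessments are listed: the VAS footnote to Protocol Table 4 ("Good Drug Effects, Bad Drug Effects, Sedated, Desire to Use Opioids VAS") and Protocol 7.2 ("Good Drug Effects, Bad Drug Effects, Sedated, and Desire to Use Opioids will be included").

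Neither scale table has a Sedated row. Protocol Table 6 and the SAP 9.0 table define one sedation-type scale, the bipolar Alertness/Drowsiness VAS, with anchors "0: Very drowsy 50: Neither drowsy nor alert 100: Very alert". Protocol 10.5 names that scale and not Sedated: "other subjective effects (Any Drug Effects, Desire to Use Opioids, and Alertness/Drowsiness VAS".

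On analysis, SAP 9.1.1 gives the only derivation of Emax, written for Drug Liking: it "of drug liking VAS will be the maximum of the above post-dosing drug liking VAS scores". SAP 9.1.2 takes the difference as test dose minus 0 mg and adds: "Blockade effects will be claimed if the upper bound of the treatment difference is" at most 11. SAP 9.2 then says of the secondary VAS endpoints: "All these variables will be analyzed via the same methodology used to analyze the primary efficacy variable". Protocol 12.3.3.2 refers to similar methods. Neither document gives a minimum-score endpoint, reverse scoring or a lower-bound rule.

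**The concern.** A reader cannot tell which scale the endpoint uses. If it is Alertness/Drowsiness, a sedated subject scores low. The maximum over the session then picks out the subject's most alert moment, and an upper bound on hydromorphone minus 0 mg guards against excess alertness. The more hydromorphone sedates, the further the difference falls and the more comfortably the rule is met. A pass on this endpoint would then say nothing about whether CAM2038 blocks sedation, and the reported effect would understate it.

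**Working it through.** **Inputs from the plan.** 24 completers per CAM2038 group, SD 9.8, margin 11, true differences 1.5 (32 mg) and 2.5 (24 mg), all in SAP 9.6. Two-sided 95% intervals are in SAP 6.0, and the 15 post-dose times in SAP 9.1.1. The SD is for Drug Liking; carrying it to another scale is an assumption.

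**The plan's own figures.** A two-sample noncentral t calculation with 24 per dose condition and two-sided alpha 0.05 gives 90.8% power at distance 11 − 1.5 = 9.5, and 83.7% at 11 − 2.5 = 8.5. The plan states 90% and about 83%. These figures are sound and do not depend on the present point.

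**Direction, from the anchors alone.** Drowsy is 0 and alert is 100. A drop in alertness can only leave the maximum post-dose score unchanged or lower it, so the expected difference (hydromorphone − 0 mg) is zero or negative.

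**Does a non-positive difference always pass?** The 95% half-width is:

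- 9.8 read as the SD of paired differences: 2.069 × 9.8/√24 = 4.1
- 9.8 read as a per-condition SD, two-sample: 2.013 × 9.8 × √(2/24) = 5.7

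An observed difference of 0 gives an upper bound of at most 5.7, below 11. On the paired reading, failing at an observed difference of 0 would need an SD above 11 × √24/2.069 = 26.

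**Probability of passing.** With SE = 9.8 × √(2/24) = 2.83, P(upper bound ≤ 11) = Φ((11 − d)/2.83 − 1.96) for a true difference d:

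| Size of true effect | Scored as written (d negative) | Scored towards sedation (d positive) |
|---|---|---|
| 0 | 97.3% | 97.3% |
| 5 | 99.99% | 56.4% |
| 10 | 100% | 5.4% |
| 20 | 100% | 0% |

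**Illustration over a time course.** All shape inputs are assumed: between-subject SD 8 around 50, 30% CV in sensitivity, a log-normal-shaped dip peaking at 60 minutes with log-width 0.6 to 1.3, reading noise SD 3, 6 or 10, integer scores from 0 to 100, paired t intervals, 2,000 runs per cell. Ranges are across noise and width.

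| True dip | Emax difference | Upper bound ≤ 11 met | Emax CI wholly below 0 | Emin difference | Emin lower bound ≥ −11 met |
|---|---|---|---|---|---|
| 15 | −1.7 to −9.1 | 100% | 48–100% | −8.6 to −13.0 | 0–26% |
| 30 | −2.3 to −15.6 | 100% | 74–100% | −19.7 to −27.0 | 0% |
| 45 | −2.7 to −20.4 | 100% | 85–100% | −27.1 to −37.2 | 0% |

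With no dip, every rule passes in 100% of runs. A second simulation (dip peaking at 45 minutes, noise SD 5, 4,000 runs) agrees. Dips of 20, 30 and 40 gave Emax differences of −4.2, −5.1 and −5.7, all passing. Scored towards sedation, they gave 15.6, 24.8 and 33.4, none passing.

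**The case against.** Five arguments can be made on the other side.

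- **Emax can mean maximum effect.** The protocol's abbreviation list expands it that way, so Emax of a Sedated VAS could mean peak sedation, with only the scoring step unwritten. That is a fair reading of intent. But SAP 9.1.1 is the only operational definition, and a programmer following it would take the highest score.
- **A pass/fail claim is inferred.** The 11-point rule sits under the primary analysis, the SAP 9.4 sequence names no secondary endpoint, and Protocol 10.5 treats the other scales as support for the primary. This stands as a limit on the consequence. Still, SAP 9.2 brings in the primary methodology without exception, and the maximum shrinks the effect even if no rule is applied.
- **Sedated may be a separate unipolar scale.** The direction would then be right. This cannot be excluded, but a listed endpoint would then lack a question and anchors in both scale tables. Protocol 10.3 points to Table 6 for the subjective measures, which favours the Alertness/Drowsiness reading.
- **The simulation inputs are invented, and the signal would often show.** Both are true. The sizes are illustrative only, and the Emax interval would often lie below zero. The direction rests on the anchors.
- **The scale has two poles.** Protocol 10.6.1 lists stimulation and restlessness among opioid effects. Under an assumed 20-point rise in alertness, the Emin rule passes in every run and the existing Emax rule fails in every run. Scoring towards sedation therefore does not cover stimulation. An endpoint named Sedated should nonetheless look towards sedation; stimulation would need its own summary.

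**Conclusion.** The point holds. It is certain that a listed secondary endpoint has no defined scale and that the documents use two names. If the scale is Alertness/Drowsiness, the analysis as written is misdirected: any observed difference at or below zero meets the 11-point rule with a half-width of 4.1 to 5.7, and the measured effect is attenuated though not hidden. This rests on that identification, on SAP 9.2 carrying the 11-point rule over, and, for the half-widths, on the Drug Liking SD of 9.8. The endpoint is outside the multiplicity sequence in SAP 9.4, so the primary conclusion does not change. It should be corrected before database lock, because choosing the scoring direction after unblinding would be post hoc.

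**What to change.** First confirm which scale is on the CRF. Then use one name throughout: Protocol Synopsis, Table 4 footnote, 7.2, 10.5, 10.7.2 and 12.3.3.2; SAP 9.2 and Tables 14.2.5.x. State its anchors.

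If it is Alertness/Drowsiness, adopt one of these two equivalent pairs:

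- Emin of the raw score, with the lower 95% bound of (hydromorphone − 0 mg) at least −11; or
- Emax of (100 − score), with the upper 95% bound at most 11.

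They are equivalent because min(score) = 100 − max(100 − score), and they gave identical pass rates in every simulated setting. They must not be mixed: the reversed score with a lower bound of at least −11 passed in 100% of runs at every dip.

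State that 11 comes from Drug Liking. Either justify it for this scale or report the difference and its confidence interval without a pass/fail rule.

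If it is a separate unipolar Sedated VAS, add its question and anchors to both scale tables.

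The cost is wording in both documents and, on the first branch, a one-line derivation. No new data are needed if the Table 6 scale is the one that was collected.
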